<http://doi.org/10.1016/j.autneu.2013.11.004>

Methods and Design

Week 1:

After telephone screening, a group of eligible participants in the same condition (HRV-increase or HR/HRV-decrease, up to 6 people) will be invited to visit the lab at the same time. 3-5 researchers will conduct this group session, which will take about 3 hours.

First, the researchers will explain the overview of the study and take any questions and concerns that they may have. This should take about 30 minutes.

Second, participants will individually fill out forms including a consent form, demographic information, and emotion questionnaires (e.g., CESD, STAI, relaxation and fatigue questionnaires). We will record their resting HRV for 5 minutes. These will take about 30 minutes.

Third, participants will be asked to complete two computer-based cognitive tasks (i.e., Stroop Task and Paced Auditory Serial Addition Test), while their heart rate, breathing, blood pressure, skin conductance and pupil size are being recorded using the lab biofeedback devices and the eye tracker. In the Stroop task, a color name (blue, green, or red) is presented on a computer monitor in a color that was either congruent or incongruent with the name. The participants' task is to press a key on the keypad corresponding to the color in which the word is presented rather than the color name. In the PASAT, the participant will be presented with single digit numbers and asked to sum the two most recent digits. The two tasks together take about 30 minutes.

Fourth, participants will be asked to complete cognitive and emotion tasks, which together take about 40 min: 1) Flanker Inhibitory Control and Attention Test, 2) List Sorting Working Memory Test, 3) Dimensional Change Card Sort Test, 4) Pattern Comparison Processing Speed Test, 5) Sustained Attention to Response Task (SART) and 6) emotion questions. The first four tests are part of the NIH Toolbox Cognition Battery. See "Watch Demo Video" in the below link for the description of each test: <http://www.healthmeasures.net/explore-measurement-systems/nih-toolbox/intro-to-nih-toolbox/cognition>

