The fifth test, SART, measures sustained attention. In this task, participants will be asked to respond to target stimuli (e.g., "3") but inhibit responding to non-target stimuli (e.g., "8" or any other digits). https://www.youtube.com/watch?v=qCrB3I_ffpU

The emotion questions are part of the NIH Toolbox Emotion Measures:

<http://www.healthmeasures.net/explore-measurement-systems/nih-toolbox/intro-to-nih-toolbox/emotion>

Lastly, phlebotomists will collect blood samples up to 25 mL via venipuncture (<http://tendertouchmobilelabs.com>). Note that blood draw volume for blood donation in the US is 1 pint (~450 mL). Thus, 25 mL should be safe for our participants.

For the rest of Week 1, participants will be asked to complete short questionnaires daily (e.g., POMS, SAI, Sleep, Stress), which takes about 5-10 minutes. In addition, they will be asked to wear a wristband that monitors their heart rate continuously until the end of the study.

After the Week 1 session, we email participants once asking to provide the details of the medications that they are currently taking (e.g., dosage, uses, ingredients). They will be asked to report any changes in medications on the following lab visits (21.2). During the following lab visits, we will also ask participants safety questions, such as "Did you notice any changes in your health or well-being this past week?" to ensure their safety and well-being throughout the study (21.2). Additionally, we will ask female participants the following questions:

- Did you have a menstrual period since your last visit?
- If so, when was the first day of your period?

Week 2:

In the morning of Week 2 visit, participants will be asked to collect saliva samples at home using provided swabs, which will take a few minutes. Participants will individually visit the lab once, which will take about 3 hours.

First, the participant will be asked to fill out emotion questionnaires (e.g., CESD, STAI), and to provide saliva samples in the lab. The participant will be asked to answer a few questions about an upcoming decision-making task, which will be administered on Week 7 (e.g., If you want to split \$10 between you and someone else, how much money do you offer to the other person?). Additionally, we will assess body measures including height, weight, waist and hip circumferences. This part will take about 20 min.

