Memory tests: Participants will be asked to view a series of pictures (i.e., NAPS or IAPS in 21.2) and rate them. Sometime later, participants will be asked to indicate whether they have seen each picture or not (recognition memory test). They will also be asked to recall pictures (recall memory test). A week later when they return to the lab, participants will be asked to indicate whether they have seen each picture or not by pressing the yes or no keys (recognition memory test). They will also be asked to recall stories that they created in the previous week (recall memory test). During the task, their heart rate, breathing and pupil size may be recorded.

Week 6:

The participants will visit the lab as a group. We will record their resting HRV for 5 min using the home devices and repeat measures from Week 1 (i.e., questionnaires, Stroop, PASAT, cognitive and emotion tasks, blood draw). As a group, the participants and researchers will discuss their experience in this study. The participants will be encouraged to share as much or as little as they would like, and the researchers will take any questions or concerns that they have. This lab visit should last about 3 hours.

For the rest of Week 6, they will be asked to continue the assigned practice for up to 20 min twice a day. Participants will also be asked to continue to fill out questionnaires and wear a wristband every day.

Week 7:

In the morning of Week 7 visit, participants will be asked to collect saliva samples at home using provided swabs, which will take a few minutes. Participants will also be asked to visit the lab individually to complete the same assessments as in Week 2. The entire visit (both the lab and MRI sessions) will take about 3 hours. In the MRI session, there will be additional scans including paced-breathing (e.g., 10 sec/breath), training-mimicking and decision-making scans. The training-mimicking scan is where we ask participants to do the biofeedback exercises that they have been practicing at home. During the decision-making scan, the participant will be asked to decide whether to accept or reject monetary offers from other participants in a decision game. At the end, they will be asked about the tasks they completed and their experiences during this study.

References

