No prior studies had examined effects of these interventions on brain function so we were unable to estimate effect sizes based on prior neuroimaging data. We elected to power our study to detect medium or larger effect sizes. Our main planned statistical comparisons were repeated-measures ANOVAs with within-between interactions. For these, a total sample size of 46 would give 90% power to detect moderate effect sizes of $f=.25$ with $\alpha = .05$, given an assumed correlation among the repeated measures of .5 (Faul et al., 2007). We also planned to examine within-subject change within each of the conditions. A sample size of 44 in each condition (HRV-increase, HRV-decrease) would give 90% power to detect within-group change effect sizes of $d=.5$ in a two-tailed t-test with $\alpha = .05$ (Faul et al., 2007). Thus, we aimed for an N=200 completion rate across the two conditions and two age groups to be able to accommodate potential exclusions for movement during imaging or other data quality issues. Due to the COVID-19 pandemic leading to increased risk for participants completing lab visits, we terminated the study before achieving our initial goal of recruiting 100 older participants.

3. Outcomes

For most outcome measures, we examined group difference (HRV-increase vs. HRV-decrease) in pre-post intervention change. The average time between pre and post intervention assessment was 5 weeks.

Primary outcome measures

- Group difference in pre-post intervention change in resting state functional connectivity between the right amygdala and medial prefrontal cortex (mPFC)

Secondary outcome measures

- Group difference in pre-post intervention change in:
 - Emotion regulation ability measured by self-reported effectiveness when instructed to regulate emotion during viewing emotional pictures
 - The ability to up- and down-regulate amygdala activity when instructed to regulate emotion during viewing emotional pictures
 - Emotional well-being measured by the Profile of Mood States (POMS), the State Anxiety Inventory (SAI), the Trait Anxiety Inventory (TAI) and the Center for Epidemiologic Studies (CES-D)
 - HRV measured by high frequency power (HF)
 - HRV measured by low frequency power (LF)

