We conducted a three-way ANOVA to examine whether emotional intensity rated by participants during emotion regulation changed after HRV biofeedback intervention for younger and older adults separately. The 2 \times 2 \times 3 ANOVA model included three factors: time-point (2 levels: pre- and post-intervention), intervention condition (2 levels: HRV-Increase, HRV-Decrease) and regulation type (3 levels: down-regulation, viewing and up-regulation). P values less than 0.05 were considered statistically significant.
- Emotion regulation (MRI analysis):
We conducted a three-way ANOVA to examine whether BOLD activity in the left and right amygdala changed during emotion regulation after HRV biofeedback intervention for younger and older adults. The 2 \times 2 \times 3 ANOVA model for each amygdala included three factors: time-point (2 levels: pre- and post-intervention), intervention condition (2 levels: HRV-Increase, HRV-Decrease) and regulation type (3 levels: down-regulation, viewing and up-regulation). P values less than 0.05 were considered statistically significant.
- Emotional well-being (pre/post):
To test whether emotional well-being changed during the course of the study and whether this depended on training condition, we performed a series of two-way mixed ANOVAs, one for each measure. In these ANOVAs, time was a within-subjects factor (2 levels: pre- and post-intervention) and condition was a between-subjects factor (2 levels: HRV-Increase, HRV-Decrease). For each ANOVA, the effect of interest was a time \times condition interaction, and only data from participants with values for both time points were included. P values less than 0.05 were considered statistically significant. ANOVAs were performed with R (Version 4.0.3) and the R package 'ez'.
- Emotional well-being (all weeks):
To test whether emotional well-being changed during the course of the study and whether this depended on training condition, we fit a series of linear mixed effects models, one for each measure. For these models, fixed effects were time (1 level per week), condition (2 levels: HRV-Increase, HRV-Decrease), and a time \times condition interaction. The models included random intercepts for participants. For each model, data from all available participants at each time point was used. To assess parameter significance, F- and p-values were determined using Satterthwaite's method. P values less than 0.05 were considered statistically significant. These

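### Each emotional well-being measure gets two unranked tests at 0.05, the pre and post weeks are not named, and the weekly model's lone random intercept can inflate its error rate

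*SAP*

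**What the plan says.** SAP section 5 introduces both well-being analyses with the same statement of purpose.

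- **Pre/post:** a mixed ANOVA per measure in which "time was a within-subjects factor (2 levels: pre- and post-intervention"). It uses complete pairs only, and the time x condition interaction is the effect of interest.
- **All weeks:** a linear mixed model per measure whose "fixed effects were time (1 level per week), condition (2 levels: HRV-Increase, HRV-Decrease") and their interaction, with a random intercept per participant and all available data.

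Each carries the rule "P values less than 0.05 were considered statistically significant". The well-being section gives no order between them and no multiplicity adjustment. It does not say which visits are pre and post.

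Elsewhere, SAP section 2 describes repeated-measures ANOVA interactions as the principal planned comparisons. SAP section 3 defines the outcome as a group difference in pre-to-post change and puts the average interval at five weeks.

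The protocol (Methods and Design) names CES-D and STAI at four visits:

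- Week 1: "demographic information, and emotion questionnaires (e.g., CESD, STAI, relaxation and fatigue questionnaires")
- Week 2, before that visit's first training session: "the participant will be asked to fill out emotion questionnaires (e.g., CESD, STAI")
- Week 6: "repeat measures from Week 1 (i.e., questionnaires, Stroop, PASAT, cognitive and emotion tasks, blood draw")
- Week 7: "visit the lab individually to complete the same assessments as in Week 2"

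POMS and SAI are also collected daily from Week 1. Home practice begins after the Week 2 visit.

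**The concern.** A reader of the results needs to know which P value decides whether training changed, say, CES-D. The well-being section allows two answers per measure, and the pre/post answer itself depends on visits that are not named. Each open choice can lift the false-positive rate above the nominal 5%.

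The weekly test has a second problem. A random intercept alone assumes that any two weeks are equally correlated. If nearby weeks are more alike than distant ones, the interaction test rejects too often even when it is the only test used.

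The weekly interaction is also a loose match to the defined outcome. With seven weekly levels it has 6 degrees of freedom. For the visit questionnaires it includes the Week 1 to Week 2 difference, which precedes training.

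**Working it through.** **1. The plan's own figure.** SAP section 2 gives N = 46 for 90% power with f = .25, alpha = .05 and correlation .5. With lambda = N f² m/(1 − rho), m = 2 occasions and df 1 and N − 2, power is 0.8997 at N = 44 and 0.9125 at N = 46, so the figure reproduces. The same formula needs only N = 30 with four occasions and N = 22 with seven, so the SAP sized a two-level pre/post ANOVA. The paired-test figure also reproduces (n = 44, d = .5: 0.900).

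**2. Two tests of one question.** The assumptions are seven weeks, complete data, two arms and no true effect, with 20,000 simulated trials per row. The weekly test is the random-intercept interaction F on 6 df.

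| Correlation between weeks (assumed) | Pre/post alone | Weekly alone | Either P<0.05 |
|---|---|---|---|
| Constant .5 | 4.8% | 5.1% | 8.6% |
| AR(1) .5 | 5.3% | 7.1% | 9.8% |
| AR(1) .8 | 4.9% | 9.0% | 10.0% |
| Part constant, part decaying | 4.8% | 7.6% | 9.6% |

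The protocol's examples do not name CES-D or STAI in Weeks 3-5, so I repeated the check with Weeks 1, 2, 6 and 7 only (N = 121, 20,000 trials). Across constant .5, AR(1) .5 and AR(1) .8, the weekly test alone gave 5.0%, 6.3% and 7.9%. Either test gave 8.0%, 8.2% and 8.9%.

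**3. Which visits are pre and post.** Week 1 to 6 and Week 2 to 7 are each five weeks apart. Week 2 to 6 is four weeks and Week 1 to 7 is six, so neither fits. The mean of Weeks 1-2 (1.5) to the mean of Weeks 6-7 (6.5) is also five weeks. For the better of the two fitting pairs, the covariance of the two changes is r(6,7) − r(2,6) − r(1,7) + r(1,2):

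- Constant .5: covariance 0, so the error is 1 − 0.95² = 9.75%.
- Adjacent weeks .8, distant weeks .5: covariance .6 and variance 1, so correlation .6 and error 8.8%.
- AR(1) .8: 1.6 − .4096 − .2621 = .928. Dividing by the variance 2(1 − .3277) = 1.345 gives correlation .69 and error 8.4%.

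Two 5% tests cannot together exceed 10%.

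**4. Would averaging help?** Take N = 121 (the younger group), a full effect of 0.4 SD (assumed) and SE² = 4V/N. Under constant r = .5, a single pair has V = 2(1 − .5) = 1.0, so SE = 0.182. The average of Weeks 6-7 minus Weeks 1-2 has V = 2(.75 − .5) = 0.5, so SE = 0.129. Under AR(1) .8 the variances are V = 1.345 (Week 2 to 7) and V = 2(.9 − .332) = 1.136.

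| True effect | Constant .5: Week 2 to 7 | Constant .5: averaged | AR(1) .8: Week 2 to 7 | AR(1) .8: averaged |
|---|---|---|---|---|
| Immediate, sustained | 0.59 | 0.87 | 0.47 | 0.54 |
| Linear build-up, Weeks 3-7 | 0.59 | 0.79 | 0.47 | 0.45 |
| Half at Week 6, full at Week 7 | 0.59 | 0.64 | 0.47 | 0.34 |
| Week 7 only | 0.59 | 0.34 | 0.47 | 0.18 |

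Under linear build-up the averaged contrast sees (0.8 + 1.0)/2 = 0.9 of the full effect, a 10% dilution. At the plan's own design effect (4f = 1.0 SD) a single pre/post pair already has 98.7% power at N = 72 and over 99.9% at N = 121.

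**The case against.** The strongest reply is that the SAP does give an order, only not in the well-being section. Section 2 makes the repeated-measures ANOVA interaction the main comparison, section 3 defines the outcome as pre-to-post change, the N = 46 calculation fits only two occasions, and the ANOVA alone carries a named effect of interest. On that reading the weekly model is supportive and the 8-10% either-test figure does not apply. This is a fair inference and it stands as one. It does not remove the wording that gives the weekly model the same purpose and threshold.

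Four stronger readings are tempting, and the documents do not support them:

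- **That the ANOVA uses one week and discards the rest.** The SAP never says so. Averaging two visits fits its words equally well.
- **That four visit pairs are open, for 12-16% error.** The five-week interval leaves two single-visit pairs.
- **That an averaged contrast would simply have more power.** This depends on trajectory and weekly correlation, which the documents do not give. The SAP's .5 was assumed for its sample-size ANOVA, not for a series of weeks.
- **That a single test gives one error rate.** It does so per measure only.

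Nothing in the documents indicates that results were selected. The rates describe what the wording allows, not what was done.

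**Conclusion.** The point holds as a matter of error control and definition. The unranked pair of tests allows about 8-10% false positives per measure, under every correlation pattern tried. The random-intercept weekly test has about 7-9% type I error by itself over seven weeks if correlation decays (AR(1) .5 to .8 or a mixed pattern), and 5% if correlation is constant. The documents do not say which pattern applies. Choosing between the two visit pairs that fit the interval allows about 8-10%.

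The case for averaging is conditional. The gain is large under roughly constant correlation with an early or steadily building effect. It is small, absent or reversed under strong decay or when the effect appears only late.

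Even with one test per measure, four measures at 0.05 give up to 1 − 0.95⁴ = 18.5% if independent. The SAP also does not say whether the age groups are tested separately for this outcome. These are secondary outcomes, so the primary connectivity test is not affected.

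**What to change.** 1. Name one decisive test per measure: the time x condition effect on pre-to-post change, which is what SAP sections 2 and 3 already point to. State the pre and post weeks, and whether visits are averaged.
2. Label the multi-df weekly interaction supportive.
3. Refit the weekly model with a covariance that lets correlation decay (unstructured or AR-type) instead of a random intercept alone.
4. For CES-D and STAI, the mean of Weeks 6-7 minus the mean of Weeks 1-2 is a reasonable choice, with its conditional power stated. For daily POMS and SAI, count only days before practice begins as baseline.
5. The SAP is dated 2024 and written in the past tense, so report the visits actually used and mark any new contrast or model as post hoc.
6. Say that error control is per measure and that the four measures are unadjusted.

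The cost is a few sentences in the SAP and a re-run on existing data, possibly with a different R package for the covariance. If visits are averaged, a linearly building effect is diluted by about 10%, and effects confined to mid-training become descriptive.

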analyses were performed with R (Version 4.0.3) and the R packages 'lmer4' and 'lmerTest'.

- HRV measured by high frequency (HF) HRV, low frequency (LF) HRV and the root mean square of successive differences (RMSSD):
To test whether HRV changed during the course of the study and whether this depended on training condition, we performed a series of two-way mixed ANOVAs, one for each measure. In these ANOVAs, time was a within-subjects factor (2 levels: pre- and post-intervention) and condition was a between-subjects factor (2 levels: HRV-Increase, HRV-Decrease). For each ANOVA, the effect of interest was a time x condition interaction, and only data from participants with values for both time points were included. P values less than 0.05 were considered statistically significant. ANOVAs were performed with IBM SPSS statistics (Version 27) and R (Version 4.0.3) with R package 'ez'.
- Inflammatory markers:
For each inflammatory marker (IL-1b, IL-6, IL-8, TNF-a, CRP), we conducted a two-way ANOVA to examine whether its levels changed after HRV biofeedback intervention for younger and older adults separately. The 2 x 2 ANOVA model included two factors: time-point (2 levels: pre- and post-intervention) and intervention condition (2 levels: HRV-Increase, HRV-Decrease). P values less than 0.05 were considered statistically significant.
- Recovery from stress:
To test whether stress recovery changed during the course of the study and whether this depended on training condition, we performed a series of two-way mixed ANOVAs, one for each measure of stress recovery. In these ANOVAs, time was a within-subjects factor (2 levels: pre- and post-intervention) and condition was a between-subjects factor (2 levels: HRV-Increase, HRV-Decrease). For each ANOVA, the effect of interest was a time x condition interaction, and only data from participants with values for both time points were included. P values less than 0.05 were considered statistically significant. ANOVAs were performed with R (Version 4.0.3) and the R package 'ez'.
- Reactivity to stress:

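### The all-weeks well-being models assume equal correlation between every pair of weeks; if correlation falls with lag, the time x condition F is mildly liberal and contrast standard errors are wrong in both directions

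*SAP*

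**What the plan says.** SAP section 5, under Emotional well-being (all weeks), fits one linear mixed model per measure, in which "fixed effects were time (1 level per week), condition (2 levels: HRV-Increase, HRV-Decrease), and a time \times condition interaction". Week is therefore categorical. On covariance the only statement is "The models included random intercepts for participants". On data: "For each model, data from all available participants at each time point was used". On inference: "To assess parameter significance, F- and p-values were determined using Satterthwaite's method", with a 0.05 threshold.

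The section states no random slope, serial residual correlation, sphericity-type correction, robust standard error or covariance sensitivity analysis. It does not give the number of weekly levels, and it names no particular week-to-week contrast.

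The same measures also have a separate pre/post mixed ANOVA with two time points. That analysis matches the outcome as SAP section 3 defines it, a group difference in pre-post change.

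**The concern.** A random intercept alone makes Week 1 correlate with Week 2 exactly as strongly as with Week 7. It therefore gives every difference between two weeks the same standard error. If neighbouring weeks are in fact more alike than distant ones, or if participants follow different slopes, one standard error cannot suit all differences. Satterthwaite's method sets degrees of freedom under the covariance that was assumed and does not repair a wrong one.

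At stake is the error rate of the time x condition F, which this analysis uses to judge whether change in well-being depended on training condition. Any contrast or trend read off the same fit is also affected. The SAP does not rank this analysis below the pre/post ANOVA. If the two disagreed, a reader could not tell a training effect from an effect of the covariance assumption.

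**Working it through.** **The plan's own figures.** The SAP gives none for the weekly model. Its power figures in section 2 do reproduce. For the interaction, the noncentrality is f² x N x m / (1 - rho) = .0625 x 46 x 2 / .5 = 11.5 on 1 and 44 df, giving power 0.912 (N = 44 gives 0.8997). For within-group change, d x sqrt(n) = .5 x sqrt(44) = 3.32, giving power 0.900. The assumed correlation of .5 is a single value and says nothing about how correlation varies with lag.

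**Inputs.** Random intercept only, categorical week and a 5% level come from SAP section 5; 121 younger and 72 older participants from section 2. Assumed: 7 weekly levels (the protocol runs Weeks 1 to 7) with 5 as the lower case, balanced data, equal variances, no true effect, and AR(1) correlation phi within persons on top of a person intercept.

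**Formula.** The model gives every week-to-week difference a variance proportional to 1 - (mean correlation over all pairs). The true variance at lag k is proportional to 1 - phi^k. Let r = model SE / true SE, the square root of that quotient. The intercept variance cancels. The actual size of a nominal 5% contrast is about 2 x [1 - Phi(1.96 r)].

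**Example, phi = .5, 7 weeks (21 pairs).** Mean correlation = (6 x .5 + 5 x .25 + 4 x .125 + 3 x .0625 + 2 x .03125 + .015625) / 21 = 5.0156 / 21 = .239.
- Adjacent weeks: r = sqrt(.761 / .500) = 1.23, size 1.6%.
- Lag 2: r = sqrt(.761 / .750) = 1.01, size 4.8%.
- Lag 3: r = sqrt(.761 / .875) = 0.93, size 6.8%.
- Lag 6 (first to last): r = sqrt(.761 / .984) = 0.88, size 8.5%.

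On a concrete scale (N = 120, total SD 1, half the variance between persons), the true SE of the group difference in change is 0.129, 0.171 and 0.181 at lags 1, 3 and 6. The model reports 0.159 for all three.

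**Range, 7 weeks.** The interaction F sizes come from 40,000 simulated null datasets.

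| phi | Adjacent weeks: r (size) | First to last: r (size) | Time x condition F |
|---|---|---|---|
| .2 | 1.08 (3.4%) | 0.97 (5.9%) | 5.3% |
| .5 | 1.23 (1.6%) | 0.88 (8.5%) | 6.9% |
| .7 | 1.37 (0.7%) | 0.80 (11.8%) | 8.5% |
| .9 | 1.54 (0.3%) | 0.71 (16.4%) | 9.7% |

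A separate simulation of 8,000 trials per scenario gave 6.4-6.6%, 8.3-8.4% and 9.4-10.3% for the F at .5, .7 and .9, and 7.9-8.0%, 11.7-11.9% and 16.4-16.8% for first to last. Sample size (72, 121 or 193) made almost no difference. A linear trend contrast is worst: r from 0.87 to 0.55, size 9% to 28%.

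**Variations.**
- Five levels: F about 5-8%; first to last about 9%, 12% and 15-16% at .5, .7 and .9.
- Week-specific noise at 30-50% of within-person variance (7 weeks, 36 per arm): F 5.4-5.8% at .5, 5.5-6.3% at .7, 5.2-5.8% at .9; first to last 6.5-9.2%.
- Random slopes instead of AR(1): with slope SD .08-.12 per week and intercept and residual variances of .5, F 4.8-5.8% and first to last 6.8-8.9%. With slope variance one tenth of residual variance, F 7.3%, adjacent r 1.18, first-to-last r 0.72.

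**After the change.** With an unstructured covariance (7 weeks, N = 72 or 120, phi .3 to .7, 2,000 datasets each), the overall test rejected 4.2-5.6% and single contrasts 4.2-6.0%.

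**The case against.** The strongest reply is that the analysis as written may be close to correct. Weekly questionnaire scores contain week-specific noise, which flattens the correlation pattern, and with a realistic share of it the F stays at 5-6%. Nothing in the documents shows that correlation falls with lag. Both points stand, and they keep the concern conditional.

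The larger figures belong to a first-to-last contrast that the SAP does not name. Its wording on parameter significance could mean coefficient tests or only the F tests for the three fixed effects, so the F is the firm target. First-to-last change is also largely covered already: the pre/post ANOVA has a single within-person difference, so this problem cannot arise there. The SAP puts pre and post about 5 weeks apart, so Week 7 against Week 1 is not even its pre-post pair. The count of seven levels is likewise an assumption. The protocol names daily POMS and SAI, but names CES-D and STAI only at Weeks 1 and 2, with those visits' measures repeated at Weeks 6 and 7.

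Three stronger readings are tempting and not supported:
- That all standard errors for change are too small. The model variance is right on average over week pairs, so adjacent-week tests are conservative.
- That the 5% level fails outright. That depends on correlations the documents do not report.
- That the use of all available data is thereby compromised. No missingness figures are given, and the calculations here use complete data.

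**Conclusion.** The covariance assumption is untested and the plan offers no check on it. If correlation falls with lag or slopes differ, the time x condition F is mildly liberal: about 5% at AR(1) .2, 6-7% at .5, 8-9% at .7 and 10% at .9 with 7 levels; about 5-8% with 5 levels; about 5-6% with substantial week-specific noise. A first-to-last by condition contrast, if one is reported, would reject about 6% at AR(1) .2 and 8-17% at .5-.9, or about 6-9% at .5-.9 with that noise. Adjacent-week contrasts err the other way.

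These sizes rest on assumed correlations, an assumed number of weeks and balanced data. The point concerns one analysis of a secondary outcome. It does not touch the primary outcome or the pre/post well-being ANOVAs. It is worth acting on because the remedy is cheap and holds whether or not correlation falls with lag.

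**What to change.** Keep the fixed effects. Refit each all-weeks model with an unstructured within-participant covariance over weeks and Satterthwaite or Kenward-Roger degrees of freedom (for example with the mmrm package in R). If a model does not converge, use a random intercept and week slope with AR(1) residuals, or cluster-robust standard errors. Report the random-intercept fit alongside and state, for each measure, whether the time x condition conclusion changes. State the number of weekly levels for each measure as well.

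The cost is a short SAP edit (the document is labelled Draft 0.2), a different R function and a re-run on data already held. With 7 weeks the covariance has 7 variances + 21 covariances = 28 parameters instead of 2, so convergence may need the fallback. P-values may move in either direction.
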